For each participant, a stimulator will be set up to stimulate finger and thumb extension in response to input from the CCFES glove. Up to 3 channels of stimulation will be used. Surface electrodes will be positioned on the forearm to activate the extensor digitorum communis (EDC) and extensor pollicis longus (EPL). Abductor pollicis brevis (AbPB), dorsal interossei (DI), or extensor indicis proprius (EIP) may also be stimulated if they are necessary to achieve functional hand opening. A maximum

stimulation intensity will be determined for each electrode, defined as the pulse width that produces maximum finger or thumb extension without discomfort. These pulse widths will be entered into a program that is then downloaded to the stimulator, ensuring that the stimulator used by each participant is customized to them.

Participant Education

After customizing the stimulator, the treating therapist will instruct and train the participants, and their caregivers if necessary, how to put on the components (i.e., electrodes, glove, and bend sensor for game play if applicable). The electrodes will be outlined on the skin and photographs of the electrodes correctly positioned will assist the subject in placing them correctly at home. An instruction manual will be reviewed with every participant, and each will be trained to operate the stimulator and HTVG (if applicable). The treating therapist will make home visits if needed to troubleshoot any problems the subjects may be having at home.

Study Treatments

The treatment regimens for both groups will last 12 weeks and consist of: a) 10 self-administered sessions per week at home, and b) 20 therapist-guided sessions in the FES Center at the LSVDVAMC (2 per week except on weeks that include an assessment visit).

Self-Administered Home Sessions

The 10 home sessions per week will be distributed so that no more than 2 sessions are done per day (separated by >2 hours), and no more than one session per day on days in which a lab session is scheduled.

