- demonstrate ability to follow instructions for operating the stimulator or have a caregiver who will assist them.

Exclusion criteria:

- co-existing neurologic diagnosis of peripheral nerve injury, Parkinson's disease, spinal cord injury, traumatic brain injury, or multiple sclerosis
- uncontrolled seizure disorder
- severely impaired cognition and communication
- uncompensated hemineglect
- arm or forearm skin breakdown or edema (to avoid edema-related shunting of current)
- insensate forearm (to avoid risk of electrical burns)
- history of potentially fatal cardiac arrhythmias
- implanted electronic systems (e.g. pacemaker)
- botulinum toxin injections to any upper extremity muscle within 3 months of enrolling
- pregnant women due to unknown risks of surface NMES during pregnancy
- participating in occupational therapy or other rehabilitation therapies to the upper extremity
- severe shoulder or hand pain

Exclusion criteria related to fMRI procedures include:

- implanted metal devices (e.g., cardiac pacemaker or defibrillator, hemostatic clips, nerve stimulators, insulin pumps, lead wires, cochlear implant, prosthetic heart valve, etc.) or indwelling metal that is incompatible with MRI (e.g., metal splinters in the orbit)
- claustrophobia
- pregnancy

Stroke survivors who do not meet the fMRI-related selection criteria but who do meet the rest of the criteria may still participate in the study, but not the fMRI procedures.

Potential Risks

Skin Irritation – When surface electrodes are used, it is possible that the subject will experience a temporary redness of the skin from either the electrodes, the conductive gel used with them, or any adhesive used to secure them. Skin irritation and redness from the electrical stimulation is also possible, but this possibility is rare and minimized by the type and intensity of stimulation that will be used. Participants will be instructed that redness should fade within an hour and that if redness persists, they should contact study staff. If necessary, electrodes or adhesives will be replaced with an alternative.

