Uncomfortable Sensation – Electrical stimulation of a muscle may be perceived as a twitching or vibrating sensation, and may be uncomfortable. Electrical stimulation of a nerve may be perceived as a strong but short shock, and may be uncomfortable. Electrical stimulation of the skin may be perceived as a “pins and needles” sensation and may be uncomfortable. Stimulus parameters will be adjusted to the subject’s comfort.

Electrical Hazards – There is a possibility of an electrical shock hazard whenever electrical stimulation is used or whenever electrical equipment is used to make measurements. There is a possibility of an electrical burn whenever electrical stimulation with surface electrodes is used. The equipment to be used has been designed and tested to minimize these risks. Subjects will be trained how to use the stimulator

safely and will be asked to adhere to a list of safety precautions. With these precautions, electrical hazards are rare.

Stimulator Malfunction: There is a rare possibility that the stimulator may malfunction and produce painful stimulation after it has been programmed in the laboratory. The sensation may be a sudden burning sensation, which can damage the skin if it does not stop. If participants experience pain from the stimulation, they are instructed to turn off the stimulator, discontinue its use, and contact study personnel.

Fatigue – During the treatment and assessment sessions, participants will practice several motor control tasks repeatedly or will be tested on how well they can move their arm and hand and perform specific tasks. These tasks involve concentration and repetition, and may induce "mental fatigue" from the intensity of concentration required during these tasks or soreness from the repetition. Participants in previous similar studies have reported feeling very tired, needing to nap when they go home, or experiencing headaches following lab sessions. This is similar to what one might experience after working hard in a traditional occupational therapy session. Participants will be given rest breaks as needed during the treatment sessions. Additionally, participants will be encouraged to plan time to rest at home after their lab sessions until they know the effect the sessions will have on them.

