If a subject experiences any of the risks described above, they will be asked to report it as soon as possible to the research team. Skin irritations, electrical burns, and electrical shocks will be assessed and treated by the study physician if necessary. In the event of skin irritations associated with the electrodes, alternative electrodes may be used and/or the use of the stimulator may be temporarily suspended. In the event of uncomfortable sensations associated with the electrical stimulation, the stimulus parameters will be readjusted to the subjects' comfort. In the event of electrical burns, the subject will be retrained in the procedures necessary to guard against their occurrence. In the event of electrical shocks, the equipment will be assessed for faults. All equipment has been designed to minimize the possibility of electrical hazards. All study staff will be informed how to reach appropriate medical personnel should an adverse event occur during treatment or assessment sessions.

Participants will be instructed in how to contact study personnel or the appropriate on-call physician should an adverse event occur while at home. There are no known lasting side effects associated with undergoing an MRI examination. Procedures in place for protecting against and minimizing potential risks include the presence of software constraints that limit the maximum deposited RF energy and the maximum magnetic gradient flux. This is a safeguard that is imbedded within the operating system of the MR imager, and will provide the same level of safeguard to the patient in this research study as is present in a conventional clinical MR examination. Therefore, these parameters will be

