within the FDA guidelines that have been developed to pose no risk to human subjects. The potential risks are also minimized by careful subject selection, excluding any patient with a contraindication to MRI (e.g. the presence of ferromagnetic metal in body, pacemaker, pregnant) from the pool of eligible subjects, and excluding any patient with a history of claustrophobia to prevent subject anxiety. To further limit any potential for discomfort, time in the scanner will be less than 1 hour. Subjects will wear noise-damping headphones to reduce exposure to MRI noise well below the FDA limit. A microphone in the headphones will allow the subject to communicate with the examiner in an emergency if he/she wants to be removed from the scanner at any time. The risk of maintaining data security will be minimized by keeping data locked in the investigators' offices and by following HIPAA regulations.

In addition to the risk management for the study described above, subjects will be given a group-specific user's manual that describes how to use the stimulator safely. This will be reviewed with each subject before they are sent home with the stimulator. The manual will list the following safety precautions:

SAFETY PRECAUTIONS:

- Avoid handling the electrodes while the stimulator is on. Always remember to turn off the stimulator before you remove the electrodes.
- Place electrodes on the skin only where instructed
- Never position electrodes on the chest, across the heart, or on the neck.
- Do not place electrodes over broken skin as this may cause a skin irritation.
- Do not submerge the stimulator in water.
- Do not use the stimulator in the bathtub or shower
- Do not operate dangerous machinery or drive while using the stimulator.
- Do not sleep while using the stimulator. Remain attentive during use to avoid skin burns.
- Use new electrodes if the reused ones no longer stick to the skin.
- Always wash and dry the skin before applying the electrodes.

- A slight reddening of the skin under the electrode is normal. This should fade after 1 hour once the electrodes are removed. If you notice redness or blistering beyond this, discontinue use and contact study personnel.
- Do not participate in this study if you are pregnant or may be pregnant; the safety of electrical stimulation in pregnancy has not been determined.

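### The burn-avoidance exclusion covers only an insensate forearm, although optional AbPB or DI stimulation would put electrodes on the hand and no hand sensation check is required: a narrow gap, cheaply closed

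*Combined protocol and SAP*

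**What the plan says.** Under Selection Criteria, the only exclusion about loss of sensation reads "insensate forearm (to avoid risk of electrical burns", so its purpose is stated along with the rule.

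Device Set Up gives the standard sites: "Surface electrodes will be positioned on the forearm to activate the extensor digitorum communis (EDC) and extensor pollicis longus (EPL". The next sentence adds that "Abductor pollicis brevis (AbPB), dorsal interossei (DI), or extensor indicis proprius (EIP) may also be stimulated if they are necessary" for functional hand opening, and gives no electrode position for these muscles. The maximum intensity for each electrode is "defined as the pulse width that produces maximum finger or thumb extension without discomfort".

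On risk, the Electrical Hazards paragraph says: "There is a possibility of an electrical burn whenever electrical stimulation with surface electrodes is used". The Stimulator Malfunction paragraph says: "If participants experience pain from the stimulation, they are instructed to turn off the stimulator". Risk Management has the study physician assess a burn, and treat it if necessary, and adds: "In the event of electrical burns, the subject will be retrained in the procedures necessary to guard against their occurrence". The safety precautions in the user's manual include "Remain attentive during use to avoid skin burns".

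**The concern.** The plan treats sensation at the electrode site as a protection against burns and writes that protection down for one region only. Two of the three optional muscles, AbPB and DI, are muscles of the hand. The third, the extensor indicis proprius (EIP), lies in the forearm and is already covered. The stated reason for the exclusion applies equally to a hand electrode, because the risk section ties the possibility of a burn to any use of surface electrodes.

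What is at stake is participant safety. Someone who cannot feel the stimulus at a hand site cannot report discomfort while intensity is being set there, and may not notice pain there if the stimulator malfunctions. Most use takes place at home with no therapist present.

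**Working it through.** No figure in the plan needs to be reproduced. The check sets the relevant texts side by side.

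1. **Region protected.** Selection Criteria names the forearm. The only exclusion that names the hand concerns severe pain, not loss of feeling.

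2. **Region that may be stimulated.** Device Set Up allows up to 3 channels. If EDC and EPL take one channel each, 3 − 2 = 1 remains; if they share one, 3 − 1 = 2 remain. How channels are shared is an assumption, but in either case a hand channel fits within the limit. The hand position is inferred from anatomy, since no site is stated for AbPB or DI.

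3. **Search for a hand sensation check.** None was found.
   - The stimulation test among the inclusion criteria concerns the finger and thumb extensors and asks for opening without pain. It is not a test of feeling, and a numb hand could pass it.
   - The Fugl-Meyer assessment, as described, rates movement.
   - The neurologic items under Baseline Variables do not name sensation, although that list is only illustrative.
   - Device Set Up and Risk Management contain no such step.
   - Excluding peripheral nerve injury does not exclude sensory loss caused by the stroke itself.

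4. **What is lost at an insensate hand site.** The intensity rule has two parts, maximum extension and absence of discomfort. The motor part still works, but the comfort part gives no information. The malfunction instruction is triggered by pain, so it may not be triggered from that site. A fault that also affected a forearm channel could still be felt at the forearm.

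5. **What remains.**
   - Device: stated limits on output, a symmetric biphasic waveform, and control through the glove on the non-paretic hand.
   - Dosing: periods of 15 minutes with 3-minute rests, and 30–50% duty cycles in the cued exercise.
   - Participant: placement outlines and photographs, visual skin checks with intact vision required, exclusion of uncompensated hemineglect, and the instruction to stay attentive.
   - Staff: therapist sessions, and home visits if needed.

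   These lower the risk, but none tells the participant in real time that a numb site is being harmed. The visual check mainly finds damage that has already begun.

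6. **Where the exposure falls.** Home: 10 sessions a week × 12 weeks = 120 sessions, and 7.5 h × 12 = 90 h. Lab: 20 sessions × about 1.5 h = about 30 h. On the prescribed schedule, home sessions are 90 / (90 + 30) = 75% of the hours. These are session hours, not stimulation time.

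The rule as written therefore lets through one specific combination: a hand channel in use, an insensate hand site and a sensate forearm.

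**The case against.** The strongest reply is that the plan seldom reaches this situation. A participant enters only if extensor stimulation already opens the hand functionally, and AbPB or DI is added only if functional opening needs it. Someone who meets the first condition should rarely meet the second. This stands, and it is the main reason the point is minor.

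The hand position is also inferred. That is true, but surface electrodes meant to activate intrinsic hand muscles have no plausible place other than the hand.

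Absence of text is weak evidence as well. The opening note says the document was extracted from the IRB protocol, and even the forearm criterion comes without a described test. A hand check may exist in text not shown, or therapists may do one as a matter of course. This stands as a limit on the point. It does not remove the point, because the forearm rule was written down with its reason and the hand site was not.

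Two stronger readings are tempting. A reader might infer that participants are being stimulated on the hand with no protection, or that a definite number face burns. The documents support neither. Several protections remain, the risk section calls electrical hazards rare when the precautions are followed, and no document gives the share with a hand channel, the share with a numb hand, or a burn rate.

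**Conclusion.** The point holds as a minor safety-wording gap. Followed exactly, the burn exclusion leaves out an electrode site that the plan permits, and at that site the comfort limit and the pain warning cannot be relied on.

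The gap probably affects few of the up to 52 participants, and possibly none. No count or risk can be derived from the documents, and none is claimed. The conclusion rests on two things: the anatomical inference about where AbPB and DI electrodes go, and the absence of a hand check from the text shown.

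A reader might also infer that people with reduced hand sensation should be kept out of the trial, or that fully intact sensation should be required at the hand. Neither follows. The existing standard bars an insensate forearm, not a partly reduced one, and the hand channel is optional. The point has no bearing on randomization, endpoints, sample size or analysis.

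**What to change.** Add one sentence to Device Set Up, after the sentence on optional muscles:

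> AbPB or DI will not be stimulated where the hand electrode site is insensate; this is checked and recorded at set-up and whenever a hand site is added.

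This applies to the hand the same standard as the forearm criterion. The exclusion list need not change, and nobody is excluded from the trial. If a hand check already exists elsewhere in the IRB protocol, citing it here is enough.

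The cost is a brief sensation check, with a record of it, for those given a hand channel. An occasional participant would lose an optional channel, but functional opening with extensor stimulation was a condition of that participant's entry.

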Lab sessions will last ~1.5 hrs. During the first 20 minutes, the CCFES group will do the repetitive CCFES-mediated hand opening exercise, with the therapist reinforcing instructions to open both hands at the same time in response to the cues. The CCFES+HTVG group will play several minutes of each of the video games they were assigned to do at home, while the therapist adjusts the difficulty levels of the games and/or introduces and teaches a new game. Then, for both groups, for 60 minutes the therapist will instruct and encourage subjects to perform functional tasks with the paretic arm and hand, using CCFES to assist hand opening during task practice. Tasks will involve hand opening and closing to pick up, manipulate, and release objects commonly used in daily life. Task difficulty will progress from easy-to-acquire-and-manipulate to tasks requiring wider hand opening, greater skill, graded hand opening (controlled release), and coordination of hand function with proximal upper limb movement.

Data Collection

Baseline Variables

A clinical coordinator will collect baseline characteristics from the participants' electronic medical record(s) and by interview. Data collected will include demographic (e.g., sex, age, race, pre-morbid hand dominance), stroke-related (e.g., time post-stroke, hemorrhagic or ischemic, cortical or subcortical, right or left, Stroke Impact Scale score), and neurologic data (e.g., side of hemiparesis, cognition, neglect, visual deficits, aphasia), as well as co-morbidities, medications, and cognitive function (Montreal Cognitive Assessment). The balance of these variables between the two groups and their effect on the outcomes will be evaluated.

Adherence

Adherence to the home regimen will be monitored with electronic data logging and participant diaries. The stimulator logs the number of cued hand opening exercise periods completed (CCFES group) and the number of CCFES-mediated hand opening/closing repetitions (both groups). The HTVG system logs game setup/difficulty settings, game performance data (e.g., scores), and number of paretic hand opening/closing repetitions. Participants will also be given a paper diary to log completion of sessions. The diaries will be reconciled with electronic data logs at every lab session, in the presence of the participant to encourage adherence.

Concomitant Therapies

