The WRAT4 (Wide Range Achievement Test 4) will be administered to all non-aphasic Candidates at the baseline visit for use in correlation data analysis. All aphasic Subjects will be administered the PPVT III (Peabody Picture Vocabulary Test) instead of the WRAT4 at baseline (0) weeks of the study at MetroHealth Medical Center for use in correlation data analysis. The WRAT4 is a verbal assessment whereas the PPVT III is a non-verbal assessment. This will allow us to gather baseline cognitive information from both our verbal and non-verbal Candidates. The subjects' impressions of the effectiveness of the intervention, the dose, and the ease of using the device/equipment, and their degree of engagement with the home sessions will be captured with questionnaires. The purpose is to gain insight into how well the device and dosage are tolerated and the subjects' perception of effectiveness. One questionnaire will be administered at all outcomes assessment visits by the blinded assessor and two others at end of treatment by a non-blinded staff member who will have no other interaction with the subjects.

Tower Test (Optional; PI Discretion)

The Tower Test is a well-known test of executive function (Shallice, 1982; Keith-Berg 2002), specifically used to detect deficits in planning. The test consists of a board with pegs and several beads with different colors. The examiner uses the beads and pegs to present the examinee with problem-solving tasks that require the examinee to move beads of different sizes and colors to the three pegs in order to match a series of configurations presented by the examiner. The performance of the examinee is compared to representative samples of individuals of the same age to derive hypotheses about the person's executive cognitive ability. The test would be administered before and after the treatment phase and at 6 months post-treatment.

fMRI Assessment

fMRI Procedure and Equipment

We will utilize blood oxygenation level-dependent (BOLD) fMRI to reveal cortical regions that are active during a motor task performed with each hand in turn. Based on our previous work,¹⁸ we will use a tracking task where patients open and close their fingers to move a cursor up and down to trace a 0.4 Hz sine wave scrolling horizontally across a screen. A mirror mounted to the head coil will allow

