Motion Sickness – There is a possibility that the video games could cause motion sickness. Some of the video games feature objects that rotate or move in a way that may cause temporary dizziness or light headedness. This risk is minimized by making the video game animation smooth and by closely matching the subjects' hand movement to what they control in the video game. Some of the video games feature less movement of objects on the screen and may therefore decrease the risk of motion sickness. Subjects will be instructed to stop playing the game if they get motion sickness. Only games that don't induce motion sickness will be used.

MRI Exam – Claustrophobia in the scanner, auditory discomfort due to noise from the magnet, and discomfort if a bite block is used to limit head movement are risks associated with the MRI procedures. Subjects with a known history of claustrophobia will be excluded from this part of the

study. The total amount of time in the scanner per session is expected to be 35 to 50 minutes; the actual scan time per session is expected to be less than 15 minutes. All MRI acquisitions, both anatomical and functional, will be performed within the FDA specified limits of magnetic field strength, gradient flux, and radiofrequency energy deposition. The MRI research scans, therefore, will be of no higher risk than a standard clinical MRI examination.

Breach of Confidentiality – There is a small risk of breach of confidentiality of subject data and protected health information.

Unknown Risks – There may be other risks as yet unknown.

Risk Management

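### Harms at home are left mainly to participant-initiated report, with no scheduled adverse event inquiry, skin check or tabulation by arm

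*Combined protocol and SAP*

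**What the plan says.** The Risk Management section sets out how harms reach the study team:

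- General request to participants: "If a subject experiences any of the risks described above, they will be asked to report it as soon as possible". The list this refers to, under Potential Risks, closes with a catch-all: "There may be other risks as yet unknown".
- Events at home: "Participants will be instructed in how to contact study personnel or the appropriate on-call physician should an adverse event occur while at home".
- Events in front of staff: "All study staff will be informed how to reach appropriate medical personnel should an adverse event occur during treatment or assessment sessions".

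The paragraph on stimulator malfunction and the safety precautions in the user's manual also tell participants to stop use and contact staff about pain, or about redness or blistering that does not settle. The motion sickness paragraph tells them to stop the game.

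Two scheduled contacts could pick up harms:

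- Adherence section: "The diaries will be reconciled with electronic data logs at every lab session, in the presence of the participant to encourage adherence". The diary is described as a log of completed sessions.
- Questionnaires section: the instruments ask about effectiveness, dose, ease of use and engagement. "The purpose is to gain insight into how well the device and dosage are tolerated", and also perceived effectiveness. "One questionnaire will be administered at all outcomes assessment visits by the blinded assessor", and two others are given at end of treatment by a non-blinded staff member.

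On the choice of cognitive tests, the same section says: "This will allow us to gather baseline cognitive information from both our verbal and non-verbal Candidates". The Selection Criteria require participants to follow 3-stage commands and exclude severe impairment of cognition and communication.

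The SAP covers motor outcomes, the effects of baseline impairment and time since stroke, and fMRI. It does not mention harms.

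**The concern.** Most treatment takes place at home without staff. For an event there to be recorded, the participant must notice it, judge it worth reporting and make contact. That is weakest for minor or slowly developing events, and for people who find speech or the telephone difficult. The protocol itself names burns, skin irritation, painful malfunction and game-induced dizziness as possible.

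Two things are at stake. The first is participant safety, because an event that nobody asks about may come to light late. The second is the comparison of arms. The trial asks what games add to CCFES, and a judgement on that needs harm counts collected in the same way in both arms. With no scheduled inquiry and no planned table, a count by arm would depend partly on who chose to report.

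**Working it through.** There is no harm rate, safety sample size or safety analysis in the documents to reproduce. The check is therefore a reading of the text, then arithmetic on the schedule, then an illustration.

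**Step 1. Each route, side by side**

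| Route | Who starts it | Scheduled? | Described as adverse event collection? |
|---|---|---|---|
| Request to report risks (Risk Management) | Participant | No | Reporting only; no recording rule |
| Contact about an event at home (Risk Management) | Participant | No | Reporting only; no recording rule |
| Contact about pain, lasting redness or blistering (Potential Risks; user's manual) | Participant | No | Reporting only; no recording rule |
| Event during a session (Risk Management) | Staff can see it | No | Staff know whom to reach; no recording step |
| Diary reconciliation (Adherence) | Staff | Every lab session | No; purpose is adherence |
| Questionnaires (Questionnaires section) | Staff | 7 assessment visits, plus 2 forms at end of treatment | No; tolerability is part of the purpose |

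Every route aimed at home events starts with the participant. The two scheduled contacts are not given an adverse event question.

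**Step 2. Exposure against contact**

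- Home sessions per participant: 10 per week × 12 weeks = 120.
- Home hours per participant: 7.5 × 12 = 90.
- Lab sessions per participant: 20 as stated. This fits 8 weeks × 2 + 4 assessment weeks × 1 = 20.
- Lab hours at about 1.5 hours each: 20 × 1.5 = 30.
- Share of treatment time at home: 90 / (90 + 30) = 75%.
- Whole trial at the maximum of 52 participants with full adherence: 52 × 120 = 6,240 home sessions, or 52 × 90 = 4,680 hours.

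The unsupervised share is large, but there are 20 existing occasions for a staff-led question.

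**Step 3. What incomplete capture could do (illustration only)**

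Let p be the true share of an arm with a given event, c the share of those cases that are recorded, and n the arm size. Then

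P(no case recorded) = (1 − p × c)^n.

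All three are assumptions. The documents give neither p nor c, and n = 26 assumes that 52 participants split equally, because the allocation ratio is not stated.

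| p | c = 1 | c = 0.5 | c = 0.3 |
|---|---|---|---|
| 10% | 0.90^26 = 6.5% | 0.95^26 = 26% | 0.97^26 = 45% |
| 5% | 0.95^26 = 26% | 0.975^26 = 52% | 0.985^26 = 68% |

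At this size an arm can show no cases of an event that is not rare, and incomplete capture makes that more likely. The table does not estimate how much will be lost in this trial.

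**The case against.** The case for the plan has real substance, and it rules out several stronger readings that a reader might infer.

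- **That harms are captured only if volunteered.** Not supported. Therapists observe the home exercise or games and then an hour of stimulated task practice at each lab session, so they can see events there. A questionnaire partly about tolerability is given at every assessment visit.
- **That only named risks are reportable.** Not supported. The list includes unknown risks, and the sentence on adverse events at home is not tied to the list.
- **That participants would keep using a harmful device.** Not supported. The instructions to stop for pain, persistent skin changes or motion sickness are explicit, and the manual is reviewed with each participant before home use.
- **That non-verbal patients are enrolled without limit.** Not supported. Candidates with aphasia are expected, but the eligibility rules require 3-stage commands and exclude severe communication impairment. Nothing shows that those enrolled could not report pain or a burn at a lab session.
- **That harms will be missed, or missed more in one arm.** Not supported. The capture rates above are assumed, and no difference in reporting between arms can be derived. Even with full capture, a 5% event goes unseen in an arm of 26 about 26% of the time, so sample size is itself a limit.

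It is also fair to say that the document describes itself as extracted from the IRB protocol, so adverse event procedures may exist elsewhere.

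After all of this, one gap remains. No scheduled contact in the text is given the job of asking about or recording adverse events, and the SAP does not plan to tabulate them. Following commands shows comprehension, which is different from being able to start and carry through a report. The caregiver mentioned in the eligibility criteria is there to help with the stimulator and has no stated reporting role.

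**Conclusion.** The point holds in a limited form. For harms at home, the plan relies mainly on participants recognising an event and contacting staff. It specifies no scheduled adverse event inquiry, no routine skin check and no table of events by arm. Treatment is mostly unsupervised (120 home sessions, about 75% of treatment time), and some participants with aphasia are expected within the eligibility limits.

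The supported conclusion is that harms may be under-recorded. The size cannot be stated from the documents. The illustration in the working rests on assumed event rates, assumed capture rates and an equal split of 52. The finding also depends on this extract being complete on safety procedures; if a fuller procedure exists, the remedy is to cite it or bring it in. This is a worthwhile, low-cost improvement, and it does not bear on the validity of the motor analysis.

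**What to change.** 1. **At each existing lab session**, during the diary reconciliation, have the unblinded therapist ask participants in both arms the same open question about any new or worsened symptom, followed by the listed risks. Record the answer even when it is no, together with the condition of the skin under the electrodes.
2. **For participants with aphasia**, use a yes/no or picture version of the same form.
3. **At weeks 24 and 36**, no unblinded contact is stated. Use a brief self-completed form that does not pass through the assessor, or extend the role of the non-blinded staff member who already gives the end-of-treatment questionnaires. The assessor then stays blinded.
4. **In the SAP**, add a descriptive table of events by arm, with the number of participants affected and the number of events. No hypothesis test is needed.
5. **Keep** the existing instructions to participants to report promptly.

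Cost: one short form and an estimated two minutes per lab session. That is 20 × 2 = 40 minutes per participant, or 52 × 40 = 2,080 minutes (about 35 hours) across the trial at full enrolment. No new visits are needed, but the week 24 and 36 inquiry takes a little extra staff time or form handling. The downside is that more minor events will be recorded and will have to be processed.
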